We propose a pilot clinical trial on the use of perioperative pregabalin in order to decrease ureteral stent related symptoms and decrease opioid usage after ureteroscopy with stent placement. Patients undergoing ureteroscopy with stent placement will receive a single dose of 300 mg pregabalin PO in the preoperative area. We will assess safety and feasibility of studying this regimen at our institution, with the aim of performing a randomized, placebo-controlled, double-blinded study in the future.

OBJECTIVES AND SCIENTIFIC AIMS

Primary Hypothesis

It is safe and feasible to study perioperative pregabalin in ureteroscopy with stent placement at our institution.

Exploratory Hypotheses

We hypothesize that the use of the perioperative pregabalin will:

- decrease ureteral stent related symptoms at 3 days post-op
- decrease the probability of a patient requiring narcotic pain medication
- decrease the total amount of narcotic pain medication used
- decrease the unplanned contact between the patient and the healthcare system related to the stent
- improve patient satisfaction after ureteroscopy with stent placement

Primary Endpoints

The primary endpoints will be as follows:

- Adverse events related to study drug
- Verified correct administration of study drug
- Correct use of study instruments

Secondary Endpoints:

Secondary endpoints include the following:

- Ureteral Stent Related Symptom Questionnaire (USSQ) [1] score at 3 days post op
- Monitored prescribing of narcotic pain medication
- Number of patients taking narcotic pain medication at several time points
- Oral morphine equivalents the patient has used at several time points
- Number of unplanned contacts between the patient and the healthcare system within 30 days
- Score on standardized evaluation of patient satisfaction

BACKGROUND AND STUDY DESIGN/INTERVENTION

The prevalence of urolithiasis is greater than 8% and increasing in the United States (US) [2]. There are several treatment options, including ureteroscopy (with or without laser lithotripsy), extracorporeal shock wave lithotripsy, and percutaneous nephrolithotomy. A recent study in California demonstrated that ureteroscopic treatment was employed in more than 40% of interventions [3], with some nationwide estimates up to 59% [4]. At least 300,000 stone

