We propose a study to extend the literature base on the use of perioperative pregabalin to ureteroscopy with stent placement through a prospective, randomized controlled trial. In order to ensure safety and feasibility of this future study, we will first perform a small pilot. We will administer study medication and study questionnaires. There will be additional components of study evaluation. This will be used to inform the design of a future trial.

CRITERIA FOR SUBJECT ELIGIBILITY

Subject Population

Undergoing elective ureteroscopy with stent placement by [name] at University of Missouri Hospital and affiliated facilities

Subject Inclusion

Age \geq 18 years

Subject Exclusion

- Renal insufficiency (eGFR $<$ 30 mL/minute/1.73 m²)
- Chronic indwelling ureteral stent
- Chronic opioid use
- History of opioid abuse
- Chronic gabapentinoid use
- Plan for inpatient hospitalization
- Pregnancy
- Inability of the patient to consent for themselves in English
- Allergy to gabapentinoid
- Liver failure or hepatic dysfunction

OVERVIEW OF STUDY DESIGNATION

Design

This is a pilot clinical trial on the use of perioperative pregabalin in order to decrease ureteral stent related symptoms and decrease opioid usage after ureteroscopy with stent placement. Patients undergoing ureteroscopy with stent placement will receive a single dose of 300 mg pregabalin PO in the preoperative area.

Pre-op standardized care

After obtaining written consent, patients will be enrolled. All patients will be told the following by a member of the study staff:

“We will be administering several medications before, during, and after your procedure to help with pain. We expect that you will be able to go home with just non-steroidal pain medication.” They will also be counseled on the risks and benefits of non-steroidal anti-inflammatory drugs (NSAIDS).

Subsequently, all patients will be given a single dose of pregabalin 300 mg PO with a sip of water approximately one hour before surgery. This will be administered per standard institutional practice. It will be recorded in the regular medical chart of the patient.

Post-op standardized care

Perioperative care, surgery and anesthesia, for all subjects will be per standard hospital protocol.

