Routine evaluation and management for those undergoing ureteroscopy with stent placement include:

ASA classification, assigned by the anesthesiologist

Deep venous thrombosis prophylaxis per standardized pathway

Estimated blood loss

Use of intraoperative fluids (crystalloid, colloid, blood products)

TOXICITIES/SIDE EFFECTS

Various symptoms have been associated with the administration of pregabalin in the perioperative setting. The risk of serious adverse events in this use of pregabalin is low [25] and the potential benefits of this treatment may outweigh the risks. This will be recorded in the PACU side effect and PACU nursing questionnaires.

Surgical complications will be assessed prospectively and retrospectively and reviewed using the institutional standard for complications reporting for all surgical patients as followed by the Department of Surgery. Standardized graded complications and adverse effects at UM utilize the five-point modified Clavien-Dindo system. Grade I include complications requiring monitoring but no intervention; Grade II requires bedside or medical treatment; Grade III constitute adverse events requiring surgical or procedural intervention with return to normal functioning; Grade IV includes disabling, life-threatening complications with resulting functional loss and grade V is death of the patient. This is a modification of the Clavien-Dindo system for reporting complications with defined, categorized and classified events that will be segregated into time periods of ≤ 30 days, 31-90 days and > 90 days after surgery and includes medication complications following NCI CTCAE version 5 guidelines.

CRITERIA FOR THERAPEUTIC RESPONSE/OUTCOME ASSESSMENT

If the surgery is aborted for any reason before placement of a ureteral stent, the patient will be removed from the study and replaced. Based on past experience these issues are rare events.

The intraoperative period is defined as the period from anesthesia induction to the extubation of the trachea. The surgical time is determined from the incision to the final skin closure.

The postoperative period is defined as the period from the extubation to various study endpoints.

Blood loss is defined as the estimate accounted from the suction device and absorptive sponges during the procedure, as described and agreed upon by the surgeon, anesthesiologist, circulating nurse, and surgical technician as covered by institutional guidelines.

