The patient's pain will be evaluated with a visual analogue scale of pain [27]. This may either be done digitally or by paper [28].

A validated questionnaire (the Ureteral Stent Symptom Questionnaire [USSQ]) exists to evaluate symptoms of ureteral stents and their effects of quality of life [1]. This will be used to evaluate how patients tolerate the stents.

Patient satisfaction will be assessed at PACU discharge as part of the patient's PACU discharge questionnaire. Similarly, satisfaction will be evaluated via questionnaires at subsequent time points.

CRITERIA FOR REMOVAL FROM STUDY

Patients will be withdrawn from the study if they express a desire to do so, if it is determined to be in the patient's best interest to do so, or if they do not undergo initiation of their surgical procedure as stipulated previously. For this pilot, if a patient fails to receive the study drug, they will be withdrawn from the study and analysis of this failure will be undertaken.

BIOSTATISTICS

Sample Size

The primary purpose of this study is to evaluate safety and feasibility of studying perioperative pregabalin at our institution, with the aim of performing a randomized, placebo-controlled, double-blinded study in the future. 10 patients will complete the study. This is a number that will allow for evaluation of potential serious side effects and feasibility. This number is also small enough that it will not waste resources or delay the future larger study. We estimate that 20 patients will need to be enrolled so that 10 will complete the study. This number of patients will be enrolled over 3 months.

Analysis

Descriptive statistics will be used in reporting patient outcomes in this pilot study. As there is no control group, significance tests will not be performed. Several questionnaires have narrative components which will be compiled and analyzed in a systematic method.

Proposed Analyses

Pre-specified parameters to be reported include the following:

- Serious adverse events
- All adverse events
- Proportion of enrolled patients completing the study
- Adverse events related to study drug
- Ureteral Stent Related Symptom Questionnaire (USSQ) [1] score at 3 days post op
- Monitored prescribing of narcotic pain medication
- Number of patients taking narcotic pain medication at several time points
- Oral morphine equivalents the patient has used at several time points
- Number of unplanned contacts between the patient and the healthcare system within 30 days

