
- Yes
- No

On what side was ureteroscopy performed?

- Right
- Left
- Bilateral
- None

Was the patient extubated in the OR?

- Yes
- No

What was the planned disposition for the patient?

[figure not shown]
- Home from PACU
- Floor
- ICU

Pacu Discharge

At one hour post op: How much pain is the patient in?

No pain

Most pain

(Place a mark on the scale above)

Where is the patient going after PACU discharge?

- Home from PACU
- Floor
- ICU

How long was it (in minutes) from when the patient arrived in the PACU until they went home?

Please indicate if the patient experienced any of the following since surgery. A check indicates that the patient did experience this adverse event.

	Yes
Dizziness	
Vertigo	
Incoordination	
Balance disorder	
Ataxia	
Diplopia	
Blurred vision	
Amblyopia	
Tremor	
Somnolence	
Confusional state	
Disturbance of attention	
Thinking abnormality	
Euphoria	
Edema	
Peripheral edema	
Asthenia	
Fatigue	
Dry mouth	
Constipation	
Amnesia	
Back pain	
Contusion	
Depersonalization	
Diarrhea	
Fall	
Headache	
Hyperhidrosis	
Increased appetite	
Infection	
Memory impairment	
Nausea	
Nervousness	
Neuropathy	
Pain	
Paresthesia	
Sinusitis	

Upper RTI

Vomiting

What are the patient's expectations regarding post-operative pain?

- There will be minimal pain regardless of treatment
- The pain regimen being given for discharge will be sufficient
- More pain medication will be required

What pain control does the patient believe they will need in addition?

- Opioid pain medication
- Non-opioid pain medication only

Aldrete

Time to Aldrete 9 or 10:

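### No denominator of all dosed patients is stated for drug-related adverse events: removal and replacement can apply after pregabalin is given, and the side-effect checklist starts at surgery rather than at the dose

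*Protocol*

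**What the plan says.** The first item under Primary Endpoints in the protocol is "Adverse events related to study drug". Under Pre-op standardized care, "all patients will be given a single dose of pregabalin 300 mg PO with a sip of water approximately one hour before surgery". Exposure therefore comes before anyone knows whether a stent will be placed.

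Three rules take patients out of the study:

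- Criteria for Therapeutic Response/Outcome Assessment sets the rule for aborted cases: "If the surgery is aborted for any reason before placement of a ureteral stent, the patient will be removed from the study and replaced". The next sentence calls such cases rare and gives no figure.
- Criteria for Removal from Study: patients are withdrawn "if they do not undergo initiation of their surgical procedure as stipulated previously". This may overlap with the first rule.
- The same section: "if a patient fails to receive the study drug, they will be withdrawn from the study and analysis of this failure will be undertaken".

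The first two can operate after dosing. Neither says what happens to the safety data of a patient who has already taken the drug.

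On reporting, Proposed Analyses lists serious, drug-related and all adverse events without a denominator; only study completion is tied to those enrolled. The SAP promises proportions with possible adverse effects and defines no analysis set.

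On collection, Toxicities/Side Effects sends drug symptoms to the PACU questionnaires. The Pacu Discharge checklist in Appendix 1 reads: "Please indicate if the patient experienced any of the following since surgery". The evaluation schedule lists no adverse event form before the PACU.

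**The concern.** A drug-safety proportion needs a stated population, and the natural one is everyone who took the drug. Here the removal rule depends on whether a stent was placed, which is settled after exposure. Because it covers an abort for any reason, it would also cover an abort caused by a reaction to pregabalin, the kind of case the endpoint exists to count.

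The checklist window is a second, separate gap. An event that begins after the dose and is over before surgery falls outside the question as worded. A patient who is dosed and then cancelled before surgery would not be expected to reach the PACU form at all.

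At stake is the main safety result of a pilot meant to inform a randomised trial. Two analysts following the current text could report different proportions from the same patients, and the later trial could inherit the wording.

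**Working it through.** **The plan's own figure.** Sample Size gives 10 completers from about 20 enrolled. That implies 50% completion, and 10/(1 − 0.5) = 20. The 50% is back-calculated from the same two numbers, so this shows only that they agree.

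**How many are dosed.** The documents do not say. The 10 are completers, and questionnaires run to one year, so patients lost during follow-up may already have been dosed, stented and assessed in the PACU. I therefore assume that the number dosed, N, lies between 10 and 20.

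**Chance that the abort rule removes a dosed patient.** No abort rate is given, so a is an assumption. P(at least one) = 1 − (1 − a)^N.

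| Assumed a | N = 10 | N = 20 |
|---|---|---|
| 1% | 1 − 0.99^10 = 9.6% | 1 − 0.99^20 = 18.2% |
| 2% | 1 − 0.98^10 = 18.3% | 1 − 0.98^20 = 33.2% |
| 5% | 1 − 0.95^10 = 40.1% | 1 − 0.95^20 = 64.2% |

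**Chance that a removed patient also had an event.** Assume a 10% event rate, unrelated to aborting, and a = 2%. Each dosed patient is then both removed and affected with probability 0.02 × 0.10 = 0.002. Over N patients this gives 1 − 0.998^10 = 2.0% or 1 − 0.998^20 = 3.9%. If events make an abort more likely, these figures rise.

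**What one removed patient does to the result** (exact 95% intervals, illustration only):

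| Removed patient | Left out | Counted |
|---|---|---|
| With an event, 10 others | 0/10 = 0% (0 to 30.8%) | 1/11 = 9.1% (0.2 to 41.3%) |
| With an event, 19 others | 0/19 = 0% (0 to 17.6%) | 1/20 = 5.0% (0.1 to 24.9%) |
| Without an event, 1 event in 10 others | 1/10 = 10.0% (0.3 to 44.5%) | 1/11 = 9.1% (0.2 to 41.3%) |

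The upper limit for 0/19 is 1 − 0.025^(1/19) = 17.6%. The error can go either way. The intervals overlap widely, but a descriptive report of no events differs from a report of one.

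**Checklist window, case by case.**

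- Event begins before surgery and persists into the PACU: can still be ticked.
- Event begins and resolves between dose and surgery: outside the question.
- Aborted after induction: the patient would presumably reach the PACU form, but the text does not say whether it is completed once the patient is removed.
- Dosed and cancelled before surgery: no scheduled form.

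**The case against.** The strongest reply is that this is silence, not a contradiction. A reader might infer that the data of removed patients are thrown away, or that the reported adverse event rate must come out too low. The documents support neither. No sentence orders deletion, and leaving out a patient without an event raises the rate. Proposed Analyses lists every adverse event, and the SAP says that descriptive statistics cover all the data. The SAP also reports the proportion who appropriately received pregabalin. Undosed patients are withdrawn, so that figure would miss them unless withdrawn patients stay in some denominators. This weakens the literal reading. It does not settle the adverse event denominator, because listing all events fixes the numerator only.

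Other routes would also catch some events. Complications are "reviewed using the institutional standard for complications reporting for all surgical patients", and that system "includes medication complications following NCI CTCAE version 5 guidelines". Serious events go to the IRB within 5 calendar days. The protocol says that potential side effects are recorded in questionnaires, and the Unanticipated Contact form prompts staff to alert study physicians to a serious drug-related event. These routes lower the risk of a missed event. None sets a denominator, and none starts the checklist at the dose.

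The promise to analyse failures of dosing is not strong evidence of a gap. It serves the separate endpoint of verified correct administration and need not have a safety counterpart.

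It is also fair to say that the window gap is about an hour long, that aborts are described as rare, and that no test or decision threshold depends on the result. All of this stands and limits the severity. I have not seen the consent form or the institutional procedures that the protocol cites; either may address data kept after withdrawal.

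**Conclusion.** The point holds as a minor one. The removal rule makes no exception for dosed patients, neither document gives a denominator for drug-related adverse events, and the checklist starts at surgery. Applying the rules as written can therefore drop or miss events on the first listed primary endpoint.

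The size is modest and rests on assumed rates. At a 2% abort rate with 10 to 20 dosed, at least one removal has a chance of about 18% to 33%, and a removed patient with an event (10% event rate, unrelated to aborting) about 2% to 4%. The change from 0/10 to 1/11 is the extreme case; if nearly all of the 20 enrolled are dosed and kept, it is 0/19 to 1/20. A reader should not conclude that the safety result would be invalid or biased in a known direction.

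**What to change.** 1. State in Criteria for Therapeutic Response/Outcome Assessment, in Criteria for Removal from Study and in the SAP that adverse events are reported as x/N over every patient who took pregabalin. This includes dosed non-completers and removed or replaced patients, as far as consent allows.
2. State that removal and replacement apply only to stent-dependent outcomes, such as the USSQ and stent satisfaction, and to the count of 10 completers.
3. Reword the Pacu Discharge checklist to ask about events since the study drug was given, and complete it for dosed patients who are cancelled or aborted.
4. List removed patients with the reason and the timing relative to the dose. The Post-op Surgeon form already allows an answer of no stent placed, so aborted cases that reach that form can be identified.

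The cost is about one sentence in each of three places, one wording change on a REDCap form, one added completion point and a short listing. A few patients would contribute adverse event data only. The target of 10 completers does not change, and no dose or clinical rule is affected.

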STATISTICAL ANALYSIS PLAN

Project Title: Perioperative pregabalin as part of a multimodal treatment plan for pain after

ureteroscopy with stent placement: a pilot

IRB Number: 2013680 Version Number: 1.1 Version Date: 11/20/2019

Principal Investigator: [name]

Funding Source: Departmental Clinical Trial Phase: Not Phased

Clinicaltrials.gov Number: NCT03927781 Study Drug/Study Device: Pregabalin

Principal Investigator	[name]	Department of Surgery Urology
		Division
Co-Investigator	[name]	Department of Surgery Urology Division
Consenting Professional(s)	Donartment of Surgery	DIVISION
Consenting Professional(s)	Department of Surgery-	
Department	Urology	

University of Missouri University Hospital Department of Surgery Urology Division [name] Descriptive statistics (counts, proportions, medians) will be used to describe all data. We will describe the demographic information of the patients enrolled and the number of patients approached to meet full enrollment. We will assess the proportion who anticipated needing opioid pain medication, who appropriately received pregabalin, who received opioid pain medication at discharge, who had emergency room visits or hospitalizations in the first 30 post-operative days, and who received opioid prescriptions within the first 30 post-operative days. We will describe the number of oral morphine equivalents prescribed. We will include median USSQ scores. We will describe proportions reporting possible adverse effects and pain level reported. All analyses will be performed in R version 3.5.1. There will be no statistical tests performed.

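### Ten completers can reveal common side effects but cannot evaluate uncommon serious ones, and neither document says whether removed or withdrawn patients stay in the safety and correct-administration proportions

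*Protocol*

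**What the plan says.** The Sample Size section of the protocol sets 10 completers and gives this reason: "This is a number that will allow for evaluation of potential serious side effects and feasibility". It adds that the number is small enough not to waste resources or hold up the later trial. On enrolment: "We estimate that 20 patients will need to be enrolled so that 10 will complete the study". No maximum is given. No event rate, precision target or threshold accompanies these numbers. The background, the toxicity section and the benefits-and-risks section describe the risk of serious events as low or very low, without a figure.

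The primary endpoints are drug-related adverse events, "Verified correct administration of study drug", and correct use of the study instruments. The dose is given about one hour before surgery. Three rules then affect who is counted:

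- If surgery is aborted before a stent is placed, "the patient will be removed from the study and replaced" (outcome assessment section, which calls this rare).
- Patients whose surgery is not initiated are withdrawn (criteria for removal).
- Under the same criteria, "if a patient fails to receive the study drug, they will be withdrawn from the study and analysis of this failure will be undertaken".

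The SAP states: "Descriptive statistics (counts, proportions, medians) will be used to describe all data". It will assess the proportion "who appropriately received pregabalin", and on safety it says: "We will describe proportions reporting possible adverse effects and pain level reported". No base is named for either proportion, and no interval is planned.

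**The concern.** The sample-size sentence credits the design with a property it lacks. A pilot of this size would probably show no serious events whether the true rate were negligible or a few per cent. If the sentence stands, a clean result could be carried into the randomised trial as evidence on serious risk.

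The missing bases matter because the removal rules act on the patients these endpoints are about. A patient removed after the dose has been exposed to the drug, and dropping that patient takes exposure, and possibly events, out of the primary safety endpoint. A patient withdrawn for not receiving the drug is a failure of the primary administration endpoint, and dropping that patient pushes the proportion towards 100%. The only pre-specified proportion in the protocol with a stated base is completion, which is out of enrolled patients.

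**Working it through.** **The plan's own figures.** The 10 has no stated derivation, so there is nothing to reproduce. The 20 is consistent with 10/(1 − 0.5) = 20, but the 50% attrition is back-calculated (1 − 10/20) and not stated.

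**How many are dosed.** Undosed patients are withdrawn, so 10 completers implies at least 10 dosed. Twenty is the enrolment estimate and not a limit. I use 10 and 20 as working values.

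**Upper limit with zero events.** The exact (Clopper-Pearson) two-sided 95% upper limit is 1 − 0.025^(1/n); the one-sided version is 1 − 0.05^(1/n). The documents plan no intervals, so the 95% level and the sidedness are my choice.

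| Dosed | Two-sided 95% | One-sided 95% |
|---|---|---|
| 10 | 1 − 0.025^(1/10) = 30.8% | 1 − 0.05^(1/10) = 25.9% |
| 20 | 1 − 0.025^(1/20) = 16.8% | 1 − 0.05^(1/20) = 13.9% |

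More dosing would not rescue the claim: at an assumed 30 dosed, the two-sided limit is 1 − 0.025^(1/30) = 11.6%.

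**Chance of seeing at least one event**, 1 − (1 − p)^n. The documents give no rate, so every p is an assumption.

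| Assumed true rate | 10 dosed | 20 dosed |
|---|---|---|
| 1% | 9.6% | 18.2% |
| 2% | 18.3% | 33.2% |
| 5% | 40.1% | 64.2% |
| 10% | 65.1% | 87.8% |
| 20% | 89.3% | 98.8% |

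The last row shows what the pilot can do: a side effect affecting one patient in five would very probably appear. At 1% or 2%, the likeliest result is no event.

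**Correct administration, assumed example.** Suppose 20 patients are due for dosing and 2 do not receive the drug.

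- Withdrawn patients counted: 18/20 = 90%. The exact two-sided 95% interval runs from the 2.5% quantile of Beta(18, 3) to the 97.5% quantile of Beta(19, 2), that is 68.3% to 98.8%.
- Withdrawn patients dropped: receipt is 18/18 = 100%.

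**Adverse events.** The number removed or withdrawn after dosing cannot be derived from the documents, so this effect cannot be sized. The side-effect checklist belongs to the PACU discharge form on the day of surgery. Patients lost at later follow-up should therefore already have a checklist. Patients whose surgery never started may not, because the form asks only about events since surgery.

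**The case against.** The strongest reply is that the protocol never promises to estimate or exclude a rate. In a descriptive pilot with no go/no-go rule, evaluation can mean looking carefully at each event that occurs; serious events are listed for reporting and go to the IRB within 5 calendar days. This has weight, and it is why the remedy is a rewording. But the word is used to justify a number of patients, and reviewing individual events does not show that 10 is enough for serious ones.

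On administration, the SAP mentions enrolled patients one sentence before the proportion, so enrolled is the natural base. The protocol also requires failures to receive the drug to be analysed. A reader might infer that the figure will be calculated on completers and so be 100% by construction. The documents do not say that, and it is the less natural reading. What stands is that neither document states that withdrawn patients remain in the proportion. Correct administration may also cover dose and timing, which could vary even among patients who received the drug.

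On adverse events, the protocol's list of analyses is not restricted to completers, and aborted surgery is described as rare. That narrows the gap but does not close it.

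Omitting intervals is a defensible choice in a small pilot, and a reader can derive them from counts, but only if the right base is reported.

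**Conclusion.** The point holds at modest severity. The stated reason for 10 completers should not extend to serious side effects: with zero events, true rates up to 30.8% (10 dosed) or 16.8% (20 dosed) are not excluded at two-sided 95%. These limits assume independent patients and full event ascertainment among those dosed. The detection probabilities also rest on assumed rates, and the 18/20 example on an assumed number of missed doses. They illustrate the issue and do not predict this trial.

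The SAP also needs to say who is counted in two primary proportions, because the removal and withdrawal rules leave this open.

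Two stronger readings are not supported. A reader might take 20 as the most that could be dosed, but it is an estimate, replacement is allowed and no maximum is set. A reader might also conclude that the pilot is too small. Its feasibility and resource reasons stand, and nothing here calls for more patients.

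**What to change.** 1. **Protocol, Sample Size.** Claim only that the number can reveal common side effects and feasibility problems. Possible wording: *This number can reveal common side effects and feasibility problems but cannot evaluate uncommon serious events. If no serious event is seen, the two-sided 95% exact upper limit for the true rate is 30.8% with 10 patients dosed and 16.8% with 20.* Report the limit for the number actually dosed, and use the same sidedness in both documents.
2. **SAP, adverse events.** Base the proportions on all patients who received pregabalin, including those later removed, replaced, withdrawn or not completing. Report both the number dosed and the number with a completed side-effect checklist, since the form may be missing for patients removed around surgery.
3. **SAP, correct administration.** Base the proportion on all enrolled patients due for dosing, and count those withdrawn for non-receipt as failures.
4. **SAP, precision.** Give two-sided Clopper-Pearson 95% intervals for these two proportions. These are estimates, so the statement that no tests will be performed can stay.

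The cost is one protocol sentence, a few SAP sentences and a few lines of R, with no additional patients. The safety statement becomes less favourable, the administration figure may fall below 100%, and checklist data may be incomplete for a few removed patients.
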